7.4.2 Statistical Analysis Plan

The statistical analysis will be performed after data finalization and database lock, following the predefined analysis sets (PPS, FAS, and Safety Analysis Set). All analyses will be conducted using standard statistical software (e.g., SPSS, SAS, or R), with the level of statistical significance set at $p < 0.05$, unless otherwise adjusted.

Efficacy Analysis

- **Primary Endpoint (Pain Score using Brief Pain Inventory):**
 - **Test: Analysis of Covariance (ANCOVA)** adjusting for baseline BPI score

- **Equivalence testing:** Pairwise comparisons using **two one-sided t-tests (TOST)** to assess whether the difference in mean change from baseline falls within the equivalence margin (± 1.0)
- **Assumptions:** Normality and homogeneity of variance will be checked. If violated, non-parametric equivalent (e.g., **Wilcoxon rank-sum test**) will be used.
- **Secondary Endpoints:**
 - **Range of Motion (ROM) and Muscle Strength:**
 - **Test:** Repeated Measures ANOVA or mixed-effects model, depending on data completeness and correlation structure
 - If non-normal: **Friedman test** or **Wilcoxon signed-rank test** for within-group, **Kruskal-Wallis test** for between-group comparisons.
 - **Thermal Sensation, Comfort, and Acceptance (ASHRAE Scale):**
 - **Test:** Chi-square test or Fisher's exact test for categorical comparisons
 - **Ordinal regression** may be used to explore patterns of thermal perception across groups.
 - **Responding Analysis (pain reduction ≥ 3 points):**
 - **Test:** Chi-square test for group-wise comparison of response rates
 - **Risk difference** and **number needed to treat (NNT)** will be calculated.

Safety Analysis

- **Adverse Events (AEs) and Adverse Drug Reactions (ADRs):**
 - **Test:** Chi-square test or Fisher's exact test for comparing incidence across groups
 - Descriptive statistics for type, severity, onset, and duration
 - **Severity grading** and **causality assessment** using **Naranjo's algorithm**.
- **Rescue Medication Use:**
 - **Test:** Poisson regression or negative binomial regression if data are overdispersed
 - Summarized as a mean number of doses used per participant and compared between groups.

Demographic and Baseline Characteristics

- **Continuous Variables** (e.g., age, BMI):
 - **Test:** One-way ANOVA or **Kruskal-Wallis test** (if non-normal distribution)
- **Categorical Variables** (e.g., sex, diagnosis):
 - **Test:** Chi-square test or Fisher's exact test as appropriate

Missing Data Handling

- **Primary Analysis** will be based on the **Per Protocol Set**, with sensitivity analysis using **Full Analysis Set (FAS)** under **intention-to-treat (ITT)** principles.
- **Multiple imputation** will be considered for missing primary endpoint data if the proportion of missing data exceeds 5%.

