4. STUDY OBJECTIVES

The objectives of this study is to demonstrate the equivalency of efficacy and safety in reducing musculoskeletal pain between Piroxicam plus Counterirritant gel versus Piroxicam gel and Diclofenac gel, applied for 6 ± 1 days in Indonesian population.

Justification:

Piroxicam plus Counterirritant, Piroxicam, Diclofenac are considered as topical Non-Steroid Anti Inflammatory Drugs (NSAIDs). Diclofenac more common to use as a standard topical treatment since they have more clinical studies data than others topical NSAIDs. To demonstrate that Piroxicam plus Counterirritant has the same efficacy with Piroxicam, Diclofenac, the dedicated clinical study need to be conducted.

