6.7 Sample Size

Assumptions

- Outcome	: Pain score
- Standard deviation (σ)	: 1.81
- Clinically meaningful margin (Δ or δ)	: 1.0
- Power	: 80% ($Z_{1-\beta} = 0.84$)
- Significance level (α)	: 0.05

Reference standard deviation from Kocak AO, Dogruyol S, Akbas I, Menekse TS, Gur STA, Kocak MB, Cekmen B, Orun S, Cakir Z. Comparison of topical capsaicin and topical piroxicam in the treatment of acute trauma-induced pain: A randomized double-blind trial. Am J Emerg Med. 2020 Sep;38(9):1767-1771. doi: 10.1016/j.ajem.2020.05.104. Epub 2020 Jun 2. PMID: 32739846.

For **equivalence trials with 3 groups**, you typically plan for **pairwise equivalence testing**:

- Diclofenac vs. Piroxicam
- Diclofenac vs. PXM plus Counterirritant
- Piroxicam vs. PXM plus Counterirritant

This means you must **adjust α** to account for **multiple comparisons**, commonly using **Bonferroni correction**:

$$\text{Adjusted } \alpha = 0.05 / 3 = 0.0167 \rightarrow Z_{1-\alpha/2} \approx \mathbf{2.39}$$

Sample Size Formula and Calculation

Using the formula for equivalence trials:

$$n = ((Z_{1-\alpha/2} + Z_{1-\beta}) \times \sigma / \Delta)^2$$

Substituting the values:

$$n = ((2.39 + 0.84) \times 1.81 / 1.0)^2$$

$$n = (4.059 \times 1.81)^2 = (7.35)^2 = 54.0$$

Sample size per group (rounded): 54

Total sample size for 3 groups: 162

With 10% dropout:

Total = $162 / (1 - 0.10) \approx 180$ participants

Recommended: 60 participants per group

The clinical study will be recruited in total 180 subjects, which means 60 subjects per arm.

Justification:

- We used the reference from Kocak et al. because: The study used topical piroxicam, which is the main active ingredient in Counterpain PXM. The study was randomized, double-blind, and controlled, and reported the standard deviation of pain scores in full—a parameter that is essential for sample size calculations. To date, we have not found any publications comparing diclofenac gel directly with topical piroxicam, with standard deviations appropriate for use in statistical calculations. So, even though the comparator was capsaicin, this reference was chosen because it is quite representative in terms of pain type and study design.

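### The level, the pairs and the success rule of the confirmatory equivalence tests are not fixed: Section 6.7 plans three pairs at 0.0167, Section 7.4.2 gives a default of 0.05 and nothing specific for the TOST

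*Protocol*

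**What the plan says.** **Objective (Section 4).** The trial is to "demonstrate the equivalency of efficacy and safety in reducing musculoskeletal pain between Piroxicam plus Counterirritant gel versus Piroxicam gel and Diclofenac gel". That names two comparisons, each involving the test gel. It does not say whether both must succeed.

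**Sample size (Section 6.7).** Three pairs are listed, and the first is "Diclofenac vs. Piroxicam". The section continues: "This means you must adjust α to account for multiple comparisons". It divides 0.05 by 3 to get 0.0167, takes the two-sided quantile 2.39, and arrives at 54 per group, or 180 in total after 10% dropout.

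**Analysis (Section 7.4.2).** The general level is given as follows: all analyses run "with the level of statistical significance set at $p < 0.05$, unless otherwise adjusted". For the primary endpoint, one bullet names ANCOVA with baseline BPI as covariate. A separate bullet names pairwise two one-sided t-tests on the difference in mean change, against a margin of ±1.0. The TOST bullet gives no level, no confidence interval, no list of pairs and no success rule. It does not say whether the tests use the ANCOVA estimate.

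**The concern.** Section 5 describes a Phase 3 confirmatory study, so its pass/fail rule should be unique before the data are seen. Here three levels for each one-sided test can be read from the text: 0.05, 0.0167 and 0.0083. They correspond to 90%, 96.7% and 98.3% confidence intervals. The same result could pass under one and fail under another, and the choice could be made after unblinding.

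The number of comparisons is also open. A three-way split spends part of the error rate on a comparison of two marketed products that the objective does not ask about. At the other extreme, 0.05 for each of several separate claims leaves the family-wise error uncontrolled.

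Finally, a TOST on raw change would forgo precision that the ANCOVA already named in the plan would give, from a baseline score that is collected anyway.

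This is not a detail left to a later document. The protocol sets a level in two places and does not connect them.

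**Working it through.** **Inputs.** From Section 6.7: SD 1.81, margin 1.0, 54 evaluable per arm. From Section 7.4.2: equivalence margin ±1.0. Assumed: true difference 0, normal data, pooled SD from three arms (3 × 54 − 3 = 159 degrees of freedom).

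**The plan's own figures.** 0.05/3 = 0.0167, and the two-sided quantile is 2.394; both reproduce. A two-sided quantile on 0.0167 means 0.0167/2 = 0.0083 in each tail, which is the third candidate level. The 54 does not follow from the line "n = ((2.39 + 0.84) \times 1.81 / 1.0)^2". The sum is 3.23, where the section goes on with 4.059. Then 3.23 × 1.81 = 5.846, squared 34.2, or 68.4 with the factor 2 for two groups. The 54 therefore cannot be used to infer which level was meant. 162/0.9 = 180 reproduces.

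**Largest observed difference that still passes.** SE = 1.81 × √(2/54) = 0.348. TOST passes when |d| < 1.0 − t × SE.

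- 0.05: 1 − 1.654 × 0.348 = 0.42
- 0.0167: 1 − 2.147 × 0.348 = 0.25
- 0.0083: 1 − 2.420 × 0.348 = 0.16

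An observed difference of 0.3 is equivalent at 0.05 and not at the other two.

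**Power by simulation, 54 per arm, test arm shared.**

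| One-sided level | Per pair | Both test-gel pairs |
|---|---|---|
| 0.05 | 78% | 63% |
| 0.0167 | 53% | 31–32% |
| 0.0083 | 35% | 15% |

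With the SD pooled over two arms only, the per-pair values are 77%, 52% and 34%. None reaches the planned 80%. With no dropout (60 per arm), the per-pair values on that two-arm basis are 83%, 61% and 45%.

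**Type I error.** The worst case for separate claims puts the test gel midway between two comparators, each one margin away. At 54 per arm the chance of at least one false claim is:

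- about 10% with each test at 0.05
- about 5% at 0.025
- about 3.3% at 0.0167

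If equivalence is claimed only when both pairs pass, each at 0.05, the error of that joint claim cannot exceed 5% (intersection-union). It was about 4% with the comparators at 1 and 0.5, 3% at 1 and 0, and 1% at 1 and 1.

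**ANCOVA or raw change.** The protocol does not say whether 1.81 is the SD of a single score or of a change, and gives no baseline-to-end correlation r. Both are assumptions here. Taking 1.81 as a single-score SD with equal variances, the ANCOVA SD is 1.81 × √(1 − r²) and the change SD is 1.81 × √(2(1 − r)).

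| r | SD, ANCOVA / change | Joint power at 0.05, ANCOVA / change |
|---|---|---|
| 0.3 | 1.73 / 2.14 | 70% / 34% |
| 0.5 | 1.57 / 1.81 | 83% / 63% |

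If 1.81 is instead the SD of change, raw change gives 63% whatever r is, and the ANCOVA SD is 1.81 × √((1 + r)/2). Joint power with ANCOVA is then 90% at r = 0.3 and 83% at 0.5. ANCOVA does better on either reading; the size of the gain depends on which one is right.

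**The case against.** **The two sections can be reconciled.** A reader might infer a flat contradiction between 0.0167 and 0.05. The documents do not support that. Section 7.4.2 allows for adjusted levels, Section 6.7 is where an adjustment is made, and both speak of pairwise tests. Reading 0.05 as the default and 0.0167 for the equivalence tests is natural. This stands, but it does not settle the matter: Section 7.4.2 never applies the exception to the TOST, and Section 6.7 itself leaves open 0.0167 or 0.0083 per one-sided test.

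**The TOST may already be adjusted.** A reader might infer that it discards the baseline adjustment. The text does not say so. An ANCOVA of change on baseline gives the same treatment difference as an ANCOVA of the final score, so a difference in mean change can be an adjusted one. The defect is that the link is not stated.

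**Bonferroni over three pairs is valid.** It is conservative (about 3.3% family-wise error in the case above), not wrong. A reader might also infer from the objective that both comparators must be matched, which would make any split unnecessary. The word joining the two comparators may equally list two separate questions, and no success rule is given. Choosing between the rules is the sponsor's decision. What stands is that a choice has to be written down.

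**Conclusion.** The point holds as an unresolved decision rule, and it should be settled before any unblinded analysis. The level, the confirmatory pairs, the success rule and the estimate behind the TOST are not fixed together anywhere in the protocol, and one planned pair lies outside the objective.

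The consequence is large. Joint power for the two comparisons in the objective runs from about 63% to 15% according to the level read, and per-pair power from 78% to 35%. If the default of 0.05 is applied to separate claims, the family-wise error reaches about 10%.

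These figures rest on SD 1.81, 54 per arm and no true difference; any true difference lowers the power. The ANCOVA comparison rests in addition on an assumed correlation and on what 1.81 measures. It shows that the choice matters but not by exactly how much.

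**What to change.** Write the same rule into Sections 6.7 and 7.4.2:

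1. The confirmatory comparisons are the test gel versus piroxicam gel and the test gel versus diclofenac gel. Diclofenac versus piroxicam is descriptive.
2. Each TOST uses the ANCOVA difference adjusted for baseline BPI and its standard error. No further covariates are needed for this point.
3. State one success rule with its level. If both comparators must be matched, test each at one-sided 0.05 (both 90% confidence intervals within ±1.0) with no split. If single-comparator claims are wanted, use 0.025 each (95% confidence intervals) or Holm over the two.
4. Restate the power in Section 6.7 at that level, and say whether 1.81 is the SD of a score or of a change.

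**Cost.** The formal diclofenac versus piroxicam claim is given up. Under the both-must-pass rule, failing against one comparator leaves no confirmatory claim. The edits are confined to two sections, but the restated power may be less favourable and the sample size may have to change. With SD 1.81, no covariate gain and the normal approximation 2Φ(1.0/SE − z) − 1, 80% power per pair needs 57 evaluable per arm at 0.05 (190 in total after 10% dropout) or 69 at 0.025 (230). Requiring 80% for both pairs jointly needs more than the per-pair number.

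### If assumptions fail, the primary equivalence test gives way to a rank-sum test with no margin, which cannot show equivalence

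*Protocol*

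**What the plan says.** Section 4 states the aim as to "demonstrate the equivalency of efficacy and safety in reducing musculoskeletal pain" between the combination gel and the two comparator gels.

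For the primary endpoint, section 7.4.2 lists three items in sequence:

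- a model: "Analysis of Covariance (ANCOVA) adjusting for baseline BPI score";
- an equivalence test: "Pairwise comparisons using two one-sided t-tests (TOST"), to see whether the "difference in mean change from baseline falls within the equivalence margin (± 1.0");
- a check and a fallback: "Normality and homogeneity of variance will be checked", followed by "If violated, non-parametric equivalent (e.g., Wilcoxon rank-sum test) will be used".

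The fallback has no margin, shifted hypothesis, interval or rule for concluding equivalence. The check has no named method or threshold, and no named variable (raw change or model residual). Sections 5.1 and 7.9.1 do not say which BPI item or composite is the primary score. Form 2 has four pain-intensity items and seven interference items, each answered by circling a whole number.

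For adverse events, section 7.4.2 gives a chi-square or Fisher's "exact test for comparing incidence across groups". No safety margin is stated anywhere.

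**The concern.** TOST rejects the hypothesis that the arms differ by 1.0 or more, so a significant result is evidence of equivalence. The ordinary rank-sum test rejects the hypothesis that the arms are the same. A significant result shows a difference, and a non-significant one shows only that none was detected. Once the fallback is in force, the plan names no result that would demonstrate equivalence. The obvious temptation is to read a large p-value as success, and that reading rewards small or depleted samples. This matters more here because the primary analysis set is the Per Protocol Set (sections 7.4.1 and 7.4.2), which can only remove participants.

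The branch also loses the baseline adjustment, since the rank-sum test has no place for a covariate. And the switch depends on a check of the data whose method is left open, so the choice of primary test could be made after the data are seen.

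The safety part of the objective has the same gap in logic: equivalence is the stated aim, but only tests of difference are listed.

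**Working it through.** **Inputs.** SD 1.81, margin 1.0, Bonferroni alpha 0.05/3 = 0.0167 and 54 evaluable per arm (60 enrolled) are from section 6.7. Significance at 0.05 unless otherwise adjusted is from section 7.4.2.

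**The plan's own figure.** The 54 does not follow from the formula as printed: 2.39 + 0.84 = 3.23, not 4.059, and (3.23 × 1.81)² = 34.2, whereas (4.059 × 1.81)² = 54.0. That is a separate matter. I take 54 as the planned number, and the argument does not depend on it.

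**Step 1: normal approximation at a true difference of 1.0.**

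- Standard error of the difference: 1.81 × √(2/54) = 0.348.
- Standardised difference for a t-test: 1.0/0.348 = 2.871.
- For the rank-sum test under normal data, multiply by √(3/π) = 0.977, which gives 2.805.
- P(not significant) at two-sided 0.05: Φ(1.960 − 2.805) = Φ(−0.845) = 0.20.
- P(not significant) at two-sided 0.0167: Φ(2.394 − 2.805) = Φ(−0.411) = 0.34.
- TOST at the margin has an error rate close to its one-sided alpha by construction: about 0.05 and 0.017.

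**Step 2: simulation with SD 1.81 and true difference 1.0.** The rank-sum columns give the proportion non-significant. The TOST columns give the proportion that wrongly declares equivalence.

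| Per arm | Rank-sum, 0.05 | Rank-sum, 0.0167 | TOST, 0.05 | TOST, 0.0167 |
|---|---|---|---|---|
| 60 | 17.4% | 31.2% | 4.5% | 1.6% |
| 54 | 21.4% | 35.9% | 4.8% | 1.4% |
| 40 | 33.6% | 51.6% | 5.0% | 1.3% |
| 20 | 63.0% | 78.5% | 1.9% | 0.0% |

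A second simulation at 54 per arm gave 21.4% and 36.8% for the rank-sum test. As the sample falls, the rank-sum reading becomes easier to pass, while TOST becomes no easier and at 20 per arm is harder.

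**Step 3: does a margin-based rank test behave?** Two one-sided rank-sum tests, with one arm shifted by +1.0 and then −1.0, declare equivalence at a true difference of 1.0 in 5.0% (alpha 0.05) and 1.4% (alpha 0.0167) of trials at 54 per arm. At a true difference of 0 their power is 73% and 46%, against 75% and 50% for the t-based TOST. So the fault is the missing margin, not the use of ranks.

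**Step 4: how often would the switch fire?** The protocol does not say what is checked, so this was simulated under assumptions: Shapiro-Wilk at 5%, 54 per arm, baseline 5 to 6 and mean reduction 2 to 4. None of these is in the protocol.

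| Score checked | Raw change, one arm | Raw change, at least one of two arms | Pooled ANCOVA residuals |
|---|---|---|---|
| One whole-number item | 57–87% | 84–99% | 21–84% |
| Mean of four pain items | 7–12% | 12–23% | 9–83% |

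The range runs from about 7% to 99%, depending on choices the protocol leaves open.

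**The case against.** The planned primary test is correct for the objective, and the defect sits in a contingent clause. The wording asks for a non-parametric equivalent and gives the rank-sum test only as an example. Coming straight after TOST and ±1.0, it could be taken to mean a rank-sum test shifted by the margin, which step 3 shows to be sound. Nor does the protocol say that non-significance will count as equivalence, so the 21% and 36% describe a reading and not a stated rule. A separate analysis plan might supply the detail.

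Part of this stands: the error rates are conditional on that reading. It does not rescue the clause. The only test named is the ordinary one, nothing attaches a margin to it, and without a margin no decision rule is left except the wrong one. The protocol itself fixes the named test for the primary endpoint, so this is not a detail merely left for later.

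Three stronger readings are tempting and are not supported:

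- **That the switch will almost always fire.** A reader might infer this from whole-number scores. It is about right only for a formal test on raw change in a single item (step 4), and the protocol fixes none of these.
- **That the ANCOVA and TOST are two competing primary analyses.** The equivalence bullet can equally be read as TOST on the ANCOVA-adjusted contrasts, and no ANCOVA p-value is offered as evidence of equivalence. It would help to say which is meant.
- **That the trial will claim safety equivalence from a non-significant test.** Safety is a secondary endpoint of recorded events and causality (section 5.2), and no such conclusion is written.

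**Conclusion.** The point holds for the fallback clause. Followed as written, it replaces a test of equivalence by a test of difference that has no margin and no baseline adjustment, and so cannot demonstrate what section 4 sets out to demonstrate. If non-significance were then taken as equivalence at a true difference of 1.0, the false support would be about 20–21% at 0.05 and 34–37% at 0.0167 (approximation and simulations together), against about 5% and 1.5% for TOST. This rests on SD 1.81, 54 per arm and that reading of the result. It needs no assumed baseline.

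How often the branch would be used is unknown. It is likely if a formal normality test is applied to raw change on one whole-number item. The fault does not depend on that frequency, because a data-driven move to a test of the wrong hypothesis is wrong whenever it occurs.

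The safety point is secondary: the objective says equivalence, while the analysis offers no margin and only tests of difference.

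**What to change.** Delete the switch from section 7.4.2 and state one decision rule. For each pair of arms, equivalence is concluded if the confidence interval for the ANCOVA baseline-adjusted difference in BPI change lies wholly within −1.0 to +1.0, whatever the normality check shows. The interval must match the chosen one-sided alpha: 90% for 0.05, or 100 × (1 − 2 × 0.0167) = 96.7% for 0.0167. With about 54 per arm and a score bounded at 0 to 10, the mean difference tolerates non-normality well. If variances differ, use robust or bootstrap intervals for the same difference and margin.

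Keep a non-parametric analysis as sensitivity only, and tie it to the margin: a Hodges-Lehmann interval judged against ±1.0, or a rank-sum TOST shifted by ±1.0.

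For safety, report adverse-event risk differences between arms with 95% confidence intervals, and state that equivalence will not be claimed from a non-significant chi-square or Fisher test. Reword section 4 to match.

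The cost is wording, with no added participants, visits or data. The safety objective becomes more modest. The change should be made before database lock.

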Range of motion (ROM) or motion arc in this study will be measured using a universal goniometer following standardized procedures to ensure accuracy and reproducibility. Each joint will be assessed in a consistent anatomical position—either supine, seated, or standing—depending on the specific joint involved (e.g., seated for elbow, supine for knee). The Principal Investigator or Sub-Investigator will perform three consecutive measurements for each motion (e.g., flexion, extension), and the average value will be recorded. Key movements assessed will include knee flexion-extension, ankle dorsiflexion-plantarflexion, elbow flexion-extension, and lumbar spine flexion or fingertip-to-floor distance for back pain. The same assessor will conduct all measurements at each time point to minimize inter-rater variability. Any limitations due to pain, guarding, or compensatory movements will be noted. ROM data will be recorded on standardized forms and used to evaluate treatment effectiveness by comparing baseline to post-treatment values against established minimal clinically important difference (MCID) thresholds.

In this study, the minimal clinically important difference (MCID) for joint range of motion (ROM) will be used to define clinically meaningful improvements in mobility following treatment. Based on validated references, the MCID values applied are $\geq 10^\circ$ for knee flexion/extension (Mizner et al., 2005) and elbow flexion-extension arc (Picha et al., 2020), $\geq 5^\circ$ for ankle dorsiflexion/plantarflexion (Cleland et al., 2013), and either $\geq 10\%$ change or ≥ 5 cm improvement for lumbar spine mobility, depending on the measurement method used (Stratford et al., 1994). These thresholds represent the minimum degree of change perceived as beneficial by patients and are appropriate benchmarks for evaluating functional recovery in musculoskeletal pain conditions.

- 3) Assessment to investigate scales on thermal sensation, thermal comfort, and thermal acceptance using ASHRAE 7-point scale questionnaire and completed with time starting the thermal sensation.

Definition:

Thermal comfort is the condition of mind that expresses satisfaction with the thermal environment and is assessed by subjective evaluation.

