Thermal sensation is assessed to determine whether a specific thermal condition can be considered comfortable or not. The most prominent scale used for the assessment of thermal sensation is the ASHRAE 7-point scale, which consists of seven verbal anchors: “cold”, “cool”, “slightly cool”, “neutral”, “slightly warm”, “warm”, and “hot”.

Thermal acceptance, refers to the degree to which a temperature range or condition is considered acceptable or tolerable by individuals.

The number of thermal sensations felt related to the product will be the result related to the participant's acceptance of the sensation.

- 4) Assessment to investigate the disappearance time of musculoskeletal pain (in days).

Definition:

To know the medication given is effective or not, we need to evaluate the musculoskeletal pain score. One of the result that can be seen is the disappearance time of musculoskeletal pain.

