7.9.2 Secondary Endpoint

The assessment of secondary endpoints will be assessed through :

- Form 3 : Pemeriksaan nyeri awal pasien
- Form 4 : Pemeriksaan indikator rasa nyeri non verbal
- Form 5 : Pemeriksaan rentang gerak
- Form 6 : Pemeriksaan kekuatan otot

By Principal Investigator or Sub Investigator on 1st Visit, 2nd Visit and 3rd Visit.

- Form 8 : thermal sensation, thermal comfort, and thermal acceptance and time of thermal sensation.

By Participant on 1st Visit, 2nd Visit and 3rd Visit.

- Adverse events symptoms, concomitant medication, rescue medication that will be described in the Diary Participant.

By Participant on Day 0 until study is completed.

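### Pain disappearance is to be timed in days, but no daily pain score is described; separately, the ROM tests do not use the joint-specific MCIDs by which ROM is to be judged

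*Protocol*

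**What the plan says.** **Pain disappearance.** The fourth secondary endpoint in Protocol Section 5.2 begins "Assessment to investigate the disappearance time of musculoskeletal pain (in days", and its explanation ties it to evaluation of the pain score. Section 7.9.1 schedules the pain questionnaire (Form 2, the BPI) at Visits 1, 2 and 3. Section 7.7.2 puts these at Day 0, Day 3 ± 1 and Day 6 ± 1. The schedule table in Section 7.9 marks primary and secondary endpoint assessment at those three visits only.

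The diary is kept throughout, with daily reminders. Its content is described three times: other symptoms and rescue medication (Section 5.2, item 1), the amount of study drug used (Section 6.13), and "Adverse events symptoms, concomitant medication, rescue medication that will be described in the Diary Participant" (Section 7.9.2).

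**Range of motion.** Section 5.2, item 2, lists the movements as "knee flexion-extension, ankle dorsiflexion-plantarflexion, elbow flexion-extension, and lumbar spine flexion or fingertip-to-floor distance for back pain". The thresholds are 10° for knee and elbow, 5° for ankle, and for the back a 10% change "or ≥ 5 cm improvement for lumbar spine mobility, depending on the measurement method used". Effectiveness is to be evaluated by "comparing baseline to post-treatment values against established minimal clinically important difference (MCID) thresholds". Section 7.4.2 gives ROM and muscle strength one entry: "Repeated Measures ANOVA or mixed-effects model, depending on data completeness and correlation structure", or, if the data are non-normal, Friedman or Wilcoxon signed-rank tests "for within-group, Kruskal-Wallis test for between-group comparisons".

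**The concern.** An endpoint expressed in days needs an observation on each day, or at least a recorded date on which pain stopped. The protocol describes neither. This is a gap in data collection, so it differs from an analysis detail that can be settled later: once participants have finished, the missing days cannot be recovered. A treatment that relieves pain a day or two sooner could then look the same as one that does not.

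For ROM, the endpoint section and the analysis section describe different quantities. The first judges change against a threshold specific to the joint. The second names tests on a measured value, without saying how a knee angle, an ankle angle and a fingertip-to-floor distance are brought together. If raw values were simply pooled, the mean would depend on the mix of diagnoses, and improvement in some back patients would count against improvement elsewhere.

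**Working it through.** The plan gives no figure of its own on this point, so the check sets the sections side by side and adds two small illustrations.

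**1. Can any described form supply the day?**
- BPI items 3 and 4 ask for the worst and least pain in the last 24 hours, and item 6 asks about pain now. A BPI on Day 3 therefore says nothing definite about Day 1, nor one on Day 6 about Day 4.
- Form 3 asks when the pain began, not when it ended.
- None of the three diary descriptions mentions pain intensity or a pain-free date.
- Section 7.9.2 names no instrument for this endpoint.

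**2. What the visits can resolve.** On nominal visit days:

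| True day of disappearance | First visit at which it is seen |
|---|---|
| 1, 2 or 3 | Visit 2 (Day 3) |
| 4, 5 or 6 | Visit 3 (Day 6) |
| 7 or later | not seen; censored |

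Within an interval, a true difference of up to 3 − 1 = 2 days is invisible. With the windows, Visit 2 can fall on Days 2 to 4 and Visit 3 on Days 5 to 7. The visit date alone can thus move the recorded day by 4 − 2 = 2 or 7 − 5 = 2 days, and the gap between the two looks can run from 5 − 4 = 1 to 7 − 2 = 5 days. The data are interval-censored, with two looks per participant.

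**3. Visit days conflict.** Section 7.7.2 first sets the return visits at Day 3 ± 1 and Day 6 ± 1. Its day-by-day flow then asks participants to return on Day 4 ± 1 and Day 8 ± 1, and later on Day 6 ± 1. The nominal gap between looks is 6 − 3 = 3 days on one reading and 8 − 4 = 4 on the other.

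**4. ROM, conditional on pooling raw values.** The inputs are the thresholds in Section 5.2. Assumptions, none from the protocol: the four non-back diagnoses are equally frequent, osteoarthritis is of the knee, all back patients are measured by fingertip-to-floor distance, and everyone improves by exactly one MCID. Improvement lowers fingertip-to-floor distance, so unsigned it enters as −5.

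Non-back mean = (10 + 5 + 10 + 10)/4 = 8.75. With back share *b*, the pooled change is 8.75(1 − *b*) − 5*b*, or 8.75(1 − *b*) + 5*b* if the sign is reversed for the back.

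| Back share | Unsigned | Sign reversed |
|---|---|---|
| 0% | 8.75 | 8.75 |
| 20% | 6.0 | 8.0 |
| 40% | 3.25 | 7.25 |
| 63.6% (= 8.75/13.75) | 0 | 6.36 |

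Every patient has improved by one MCID in every row. Correcting the sign removes the cancellation, but the mean still adds degrees to centimetres and still moves with case mix. Counting MCID responders gives 100% in every row.

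**The case against.** The strongest reply on ROM is that Section 7.4.2 names a family of models and is silent on pooling. Models per joint, a joint term or a sign convention could all stand in a statistical analysis plan that is not at hand. Section 5.2 also words the lumbar threshold as an improvement, which implies a direction. This stands: a reader might infer that one model is to be fitted to raw values across all joints, but the document does not say so, and the table above shows only what would follow if it were done. What remains is that Section 5.2 commits to an MCID comparison and the tests in Section 7.4.2 do not carry it out.

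On pain disappearance, three replies have force.
- The diary form is not reproduced, so it might contain a pain item. The supportable statement is that no section describes one.
- A reader might conclude that the endpoint can take only the values Day 3 and Day 6. The ± 1 day windows rule that out: the recorded day can be any from 2 to 7.
- A reader might add that Section 7.4.2 gives this endpoint no test. That is detail an analysis plan may hold, and it is not part of this point.

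Nor can either endpoint be called unreadable. ROM can be read per joint or as MCID responders, and disappearance can be read as the proportion pain-free at each visit or as interval-censored time. Disappearance cannot be read as a time in days.

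**Conclusion.** The main point holds: the data collection described cannot deliver a time to pain disappearance in days. It gives two looks per participant, nominally 3 days apart in a trial of about 6 days, and a later analysis plan cannot make up the loss. This assumes that the diary contains what the sections say it contains.

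The ROM point holds in a narrower form. The stated criterion (joint-specific MCIDs in differing units) and the stated tests do not match. Mixing of units and direction is a risk if raw values are pooled, not something the protocol prescribes, and the size shown depends entirely on the assumed case mix.

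Both endpoints are secondary, and the primary equivalence comparison does not rest on them. The disappearance endpoint should be repaired first, because it can be repaired only while data are still being collected.

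**What to change.** **Pain disappearance.** Add one daily 0–10 pain line to the existing diary. Define disappearance, for example as the first day with a score of 0, with any rescue use on that day recorded. Analyse time to that day, censored at the last diary day. Because the objective is equivalence, report between-arm estimates with confidence intervals; a non-significant test of difference would not be enough. If the diary is left unchanged, restate the endpoint as the proportion pain-free at Visit 2 and at Visit 3, or analyse it as interval-censored. Reconcile the visit days within Section 7.7.2, since they set the intervals. The cost is one more entry per day and an amendment, which under Section 7.11.2 needs agreement between sponsor and investigator and ethics approval.

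**ROM.** Either make the analysis the proportion reaching the joint-specific MCID of Section 5.2, stratified by joint or diagnosis, or model change per joint, signed so that positive means improvement. Record the measurement method for back patients, because the lumbar threshold depends on it. State how areas without a listed threshold are handled: Section 6.8 names hand, wrist and shoulder among the treated areas, and Section 5.2 gives no MCID for them. The cost is a change of wording and, for the responder analysis, some information lost by dichotomising.
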